## **2. LIST OF ABBREVIATIONS**

---

Term	Definition / description
AE	Adverse Event
BRPM	Blinded Report Planning Meeting
CR	Complete Response
CRF	Case Report Form
CTC	Common Terminology Criteria
CTP	Clinical Trial Protocol
DCR	Disease Control Rate
DOR	Duration of Response
ECOG	Eastern Cooperative Oncology Group
EGFR	Epidermal Growth Factor Receptor, also known as ERBB1
EMA	European Agency for the Evaluation of Medicinal Products
ERBB2	Second member of the ERBB family of proteins
ERBB3	Third member of the ERBB family of proteins
HLT	High Level Term
ICF	Informed Consent Form
ICH	International Conference on Harmonisation
IPV	Important Protocol Violations
MedDRA	Medical Dictionary for Regulatory Activities
MQRM	Medical Quality Review Meeting
NCI	National Cancer Institute
NE	Not Evaluable
NN	Non-CR/Non-PD
ORR	Objective Response Rate
OS	Overall Survival
PD	Progressive Disease
PDL1	Programmed Death Ligand 1
PFS	Progression Free Survival
PK	Pharmacokinetics
PSTAT	Project Statistician
PR	Partial Response

---

PT Preferred Term

---

Proprietary confidential information © 2018 Boehringer Ingelheim International GmbH or one or more of its affiliated companies

---

Term	Definition / description
PV	Protocol Violation
RECIST	Response Criteria for Solid Tumours
SD	Stable Disease
SMQ	Standardised MedDRA query
TOC	Table of Contents
TMW	Trial Medical Writer
TSAP	Trial Statistical Analysis Plan

---

### **3. INTRODUCTION**

As per [ICH E9](#), the purpose of this document is to provide a more technical and detailed elaboration of the principal features of the analysis described in the protocol, and to include detailed procedures for executing the statistical analysis of the primary and secondary variables and other data.

This TSAP assumes familiarity with the Clinical Trial Protocol (CTP), including Protocol Amendments. In particular, the TSAP is based on the planned analysis specification as written in CTP Section 7 “Statistical Methods and Determination of Sample Size”. Therefore, TSAP readers may consult the CTP for more background information on the study, e.g., study objectives, study design and population, treatments, definition of measurements and variables, planning of sample size.

The validated SAS® version will be used that is in place on the BI system at the time of analyses. Currently Version 9.3 is being used.

#### **4. CHANGES IN THE PLANNED ANALYSIS OF THE STUDY**

The protocol was amended to modify the futility analysis criterion to assess ORR as well as PFS6. This amendment is reflected in Sections [7.4](#) and [7.5.1](#) of this document.

## **5. ENDPOINTS**

### **5.1 PRIMARY ENDPOINT**

This is an open label, uncontrolled, exploratory phase II trial with two patient cohorts. The purpose of this trial is to assess the anti-tumour activity and safety of afatinib monotherapy in patients with urothelial tract carcinoma carrying ERBB2 or ERBB3 mutations or ERBB2 amplifications (Cohort A), and EGFR amplification positive tumours (Cohort B), progressing despite previous platinum based chemotherapy, and thereby to improve their prognosis.

Cohort A of the study follows a two stage design where an analysis for futility will be performed at the end of stage 1 to determine if the stage 2 of cohort A will be carried out. Cohort B of the study will include up to 10 patients with EGFR amplification. Analysis will be conducted in parallel to, and independent of cohort A.

The primary endpoint of this study is progression-free survival rate at six months (PFS6), as assessed at the investigative sites, in the ERBB2/ERBB3 cohort (Cohort A). Patients who are alive and progression-free at the 24-week assessment will be considered successes.

RECIST 1.1 (2) will be used to determine all response and progression endpoints.

### **5.2 SECONDARY ENDPOINTS**

#### **5.2.1 Key secondary endpoint**

- The key secondary endpoint for the ERBB2/ERBB3 cohort (Cohort A) is confirmed objective response rate (best overall response of CR or PR) by investigator review.

#### **5.2.2 Other secondary endpoints**

Refer to Section 5.1.2 of the CTP.

Other secondary endpoints for the ERBB2/ERBB3 cohort are:

- Progression-free survival (PFS)
  - Defined as the time from the treatment start date to the date of disease progression, or to the date of death if a patient died earlier
- Overall survival (OS)
  - Defined as the time from the date of treatment start date to the date of death

---

Proprietary confidential information © 2018 Boehringer Ingelheim International GmbH or one or more of its affiliated companies

- Disease control rate (best overall confirmed response of CR, PR, or SD)
- Duration of confirmed objective response
- Tumour shrinkage

## 6. GENERAL ANALYSIS DEFINITIONS

### 6.1 TREATMENTS

For reporting purposes, patients in the ERBB2/ERBB3 cohort will be presented separately from those in the EGFR cohort.

The following study periods based on actual start and stop dates of afatinib administration are defined:

- Screening: day of informed consent to day prior to starting afatinib.
- On-treatment: day of first administration of afatinib to the last administration of afatinib.
- Residual effect period: day after last administration of afatinib to the 30th day after last administration of afatinib.
- Post-study: on or after the 31st day after last administration of afatinib.

Data from the on-treatment and residual effect periods will be included in the safety analyses.

### 6.2 IMPORTANT PROTOCOL VIOLATIONS

Patients with potentially important protocol violations (IPVs) will be documented. The following list of potentially IPV's will be used; note that this is a working list and may not be finalised until the final Blinded Report Planning Meeting (BRPM) prior to database lock.

Table 6.2: 1 Important protocol violations

Category/code	Description	Comment	Manual/ Automatic
A	Entrance criteria not met		
A1	Diagnosis of urothelial tract carcinoma questionable	Refer to IN 2,3	Automatic
A2	Prior treatment for urothelial tract carcinoma does not meet entrance criteria	Refer to IN 4,5, EX 1,2 Should have received one line of prior systematic chemotherapy in metastatic set up. This needs to be platinum based therapy. Check for patients with no prior systematic platinum based therapy or more than one line of prior systematic therapies as well.  Also check exclusion criterion 1 and 2.	Manual/Automatic
A3	Prior surgery and radiotherapy do not meet entrance criterion	Refer to EX 3, 4. Major Surgery within 4 weeks before starting study treatment, Radiotherapy within 4 weeks prior to start of study treatment in non-palliative setting.	Manual/Automatic
A4	No measurable disease according to RECIST 1.1 at screening	Refer to IN6	Automatic

Table 6.2: 1 Important protocol violations (Contd.)

Category/code	Description	Comment	Manual/ Automatic
A5	No evaluable biopsy obtained at screening	Refer to IN9	Manual
A6	Patients not correctly classified according to EGFR, ERBB2, and ERBB3 status at screening	Refer to IN10	Manual
A7	Abnormal screening values	Refer to IN11	Automatic
A8	ECOG PS is not 0 or 1	Refer to IN7	Automatic
A9	Other deviation from entrance criteria	Refer to in/exclusion criteria	Manual
B	Informed consent		
B1	Informed consent not available	Signed informed consent not available	Manual
B2	Inadequate informed consent	Informed consent obtained but not adequately done (e.g., obtained after the study specific activities were done, patient signed the wrong version of the ICF, and version signed did not receive prior IRB/IEC approval).	Manual
C	Trial medication		
C1	Incorrect medication dose taken	e.g., starting dose is not 40 mg for afatinib; dose was not paused, resumed, reduced, or discontinued according to protocol	Manual
C2	Non-compliance	Check MQRM listings for extreme non-compliance only	Manual
D	Concomitant medication		
D1	Use of prohibited concomitant medications	Review concomitant medications for prohibited medication use.	Automatic
E	Trial specific		
E1	Week 24 response assessment not performed according to protocol	Week 24 imaging and response assessment expected but not performed OR Week 24 imaging and response assessment performed before Day 140	Automatic
E2	Procedures not performed according to protocol	Check applicable data.	Manual
E3	Prohibited anticancer interventions	Patient received therapeutic radiation or another anti-cancer treatment before termination of afatinib	Manual

### **6.3 PATIENT SETS ANALYSED**

Treated set: this includes all patients who received at least one dose of afatinib.

The treated set will be used for all efficacy and safety analyses.

### **6.5 POOLING OF CENTRES**

This section is not applicable because centre/country is not included in the statistical model.

### **6.6 HANDLING OF MISSING DATA AND OUTLIERS**

Missing efficacy data will not be imputed and all reasonable efforts will be taken during the study to obtain such data. Patients with unknown vital status or time to progression will be censored for time to event analyses; further details are provided in Section 7.

Missing or incomplete AE dates are imputed according to BI standards (see “Handling of missing and incomplete AE dates”). (3)

## **6.7 BASELINE, TIME WINDOWS AND CALCULATED VISITS**

Baseline values will be the measurements taken most recently prior to first dose of afatinib.

Study day will be calculated relative to the date of the first administration of afatinib. The day prior to first administration of afatinib will be 'Day -1' and the day of first administration of afatinib will be 'Day 1'; therefore 'Day 0' will not exist.

Imaging will be performed at 8, 16 and 24 weeks, and in 12-weekly intervals thereafter; images will be slotted to the planned time based on their relative day and using a  $\pm 4$  week window as appropriate (images taken in the first 4 weeks from afatinib initiation will be slotted to Week 8). If two or more images for a patient are assigned to one interval then the last assessment will be used to ensure progressive disease is not missed.

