12. Safety lab tests to be performed as described in [Section 5.3.3](#), but should not be repeated if previous tests are older than 48 hours
13. Mandatory for female patients of child bearing potential (post menarchal) within 7 days prior to first treatment and at EOT. To ensure early detection of pregnancy, test might be repeated as necessary during the treatment period depending on the local law
14. ECG is required at screening, at C1V2, and V1 of every third course thereafter (i.e. C4V1, C7V1...) and EOT
15. Tumour assessment by Imaging (CT or MRI) should be performed every 8 weeks (+/- 1 week) calculated from the first treatment day to the end of study treatment. If treatment discontinuation is for other reason than disease progression, further tumour assessments should be obtained as follows: every 8 weeks (+/-1 week) until month 6, and every 12 weeks (+/-2 weeks) from 6 months onwards, until documented progression of disease. Baseline CT/MRI must be performed within 28 days before start of study treatment (if an assessment was performed within this timeframe, patient would not need to repeat this test).
16. Blood and urine for biomarker testing will be collected at screening, then every 4th cycle during treatment, and also at End of Treatment. If a patient has not progressed at End of Treatment then samples should continue to be collected at every 4th follow-up visit and also at the last follow-up visit (as described in [Section 5.5](#)).
17. Pharmacogenetics: one optional blood sample, to be obtained only after signing of PGx consent at any treatment visit.
18. New kit(s) of trial drug must be dispensed at visit1 of each course. If needed (e.g. in case a dose adaptation has to be applied during treatment course), new kit(s) of trial drug might be dispensed outside of the planned visit schedule
19. AE/SAE should be reviewed at every treatment visit, at EOT, EOR and thereafter as described in [section 5.3.6](#).
20. Conclusion of patient participation: should be recorded at the last follow-up visit, when PD/Death occurs, consent withdrawal or death
21. All patients will be followed-up for overall survival at 90 days intervals. For patients who progressed on treatment, the observation period for overall survival starts after the EoR. For patients who have not progressed on treatment, this period starts after the last follow-up for progression visit. The End of the Trial will be achieved as described in [Section 8.6](#).

TABLE OF CONTENTS

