5.2 ASSESSMENT OF EFFICACY

Response and progression will be evaluated in this study using Response Evaluation Criteria in Solid Tumours (RECIST) guideline (version 1.1) ([R09-0262](#)). Tumour response will be assessed by investigator review. Images will be stored in case independent radiology review may need to be introduced at stage 2.

It is critical to continue response evaluation until progression if patients withdrew consent from continuation of treatment but agreed to participate in follow-up tumour assessment.

See [Appendix 10.5](#), RECIST 1.1 Criteria for details on lesion measurements and response assessment.

Tumour assessment by Imaging (CT or MRI) should be performed at screening, and then every 8 weeks (+/- 1 week) calculated from the first treatment day to the end of study treatment . If treatment discontinuation is for other reason than disease progression, further tumour assessments should be obtained as follows: every 8 weeks (+/-1week) until month 6, and every 12 weeks (+/-2 week) from 6 months onwards, until documented progression of disease.

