6.2.2 Treatment period(s)

Every treatment course is defined as 28 days. All subsequent visit dates should be calculated based on Course 1 Visit 1 date. If a visit is missed there will be no re-scheduling; if a patient should attend the study site between the “missed” and the next scheduled visit, then the missed visit assessments should be performed.

The investigations are outlined in the [Flow Chart](#) and will be performed at the respective visit, but are described in detail in the following sections.

During the first visit of each treatment course, the following procedures will be performed:

- Physical examination: complete medical examination including body weight
- ECOG performance status
- Vital signs
- Safety lab: haematology, biochemistry, coagulation parameters and urine analysis as described in [Section 5.3.3](#).
- Dispense study medication, and dose assessment
- Review of adverse events and concomitant medication

During Course 1, an additional visit will be performed 8 days after the start of treatment (C1V2). The main objective of this visit is to assess the safety profile of trial drug. The exact procedures to be done are described in the study [flowchart](#).

Additionally, a patient contact is to be done 15 days after starting study medication, and one week after starting treatment Course 2, to check for adverse events and concomitant medication. Information for these contacts could be collected by phone. A formal visit is not required if not needed.

Additionally, the following procedures will be done at specific timepoints:

- 12-lead ECG, to be performed at screening, C1V2, C4V1, and every third course thereafter (C7V1, C10V1,...)
- At the end of second treatment cycle, i.e. 8 weeks after the start of study medication and every 8 weeks thereafter, tumour imaging to assess response to treatment must be

performed. In case of objective response, the latter has to be confirmed 4 to 6 weeks after initial OR observation.

- A plasma and an urine sample will be stored for exploratory analyses – for details see [Section 5.5](#).

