7.7 DETERMINATION OF SAMPLE SIZE

[Table 7.7: 1](#) shows that 70 patients would be expected to provide approximately 90% power for PFS6, with PFS6=60% under the alternative hypothesis and PFS6=40% under the null. Although the Stage 1 futility criterion will reduce the power, the power after adjustment for the futility analysis would likely be between the unadjusted and adjusted power estimates in [Table 7.7:1](#), because the futility criterion allows the trial to proceed to Stage 2 with fewer than 12 patients with successful PFS6, provided at least two patients have confirmed response.

Table 7.7: 1 Power¹ for PFS6 in Cohort A, with PFS6=60% under the alternative hypothesis.

	N=65	N=70	N=75
Without adjustment for Stage 1			
alpha=0.025	87.2%	90.9%	93.6%
alpha=0.050	91.7%	94.3%	96.0%
With adjustment for Stage 1 (N=25, PFS6≥12)			
alpha=0.025	83.5%	86.3%	88.2%
alpha=0.050	87.1%	88.8%	89.9%

¹Based upon simulating one million samples under the alternative hypothesis of PFS6=60%. For each sample a significance level was calculated as the binomial probability ($X \geq s | n, p=0.40$), where 's' is the observed number of patients achieving PFS6 and 'n' is the total number of patients.

Table 7.7: 2 shows that 70 patients would be expected to provide approximately 80% power for ORR, with ORR=15% under the alternative hypothesis and ORR=5% under the null.

Tables 7.7:1 and 7.7:2 present power for both alpha=0.025 and 0.05 because the Hochberg multiplicity procedure would compare the higher of the observed significance levels for PFS6 and ORR to 0.05. If the larger significance level is smaller than 0.05, then we can reject null hypothesis for both PFS6 and ORR. If the larger significance level is greater than 0.05, then the smaller significance level would be compared to a more stringent threshold 0.025, in order to refrain the family-wise error rate at 0.05.

If the underlying PFS6 rate is 40%, the probability of observing fewer than 12 patients out of 25 in Stage 1 would be 73%. Under the alternative that PFS6=60%, the chance of observing at least 12 patients would be 92%.

For ORR under the null ORR=5%, the probability of observing fewer than 2 confirmed responses in Stage 1 would be 64%. Under the alternative that ORR=15%, the chance of observing at least 2 responses would be 91%.

For Cohort B the analyses will be exploratory and descriptive in nature and the sample size is determined based on feasibility and practical considerations.

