10.5 APPENDIX 5: RECIST 1.1 CRITERIA

The criteria below are based on RECIST 1.1 ([R09-0262](#)).

The preferred method of assessment is a spiral CT scan with IV and oral contrast, unless IV and/or oral contrast are medically contraindicated. CT scans of the chest, abdomen and other areas of known or newly suspected disease must be performed. Scans of the abdomen, pelvis and other areas of the body, but not chest, may be done with MRI instead of CT.

Skin lesions followed as target lesions must be documented by colour digital photography and must include in the image a ruler with millimetre subdivisions and a label that includes the patients ID and date.

Bone scans (using ^{99m}m-technetium polyphosphonate scintigraphy) are recommended at baseline if the patient has any signs and symptoms consistent with bone metastasis or a

history of bone metastasis. Bone metastasis identified at baseline must be documented and assessed according to RECIST 1.1 at the times of the other tumour measurements indicated in the [flow chart](#). During the study bone scans should be repeated as clinically indicated in patients without bone metastasis at Baseline.

For the purposes of this study, patients should be re-evaluated for response at weeks 8, 16, 24 and every 8 weeks thereafter. In the event of a treatment delay, interruption or discontinuation of treatment, tumour assessment should continue to follow the original schedule.

Follow-up tumour assessments must utilize the same CT/MRI/photographic method and acquisition technique (including use or non-use of IV contrast) as were used for screening assessments to ensure comparability. A chest x-ray or skeletal x-ray which clearly demonstrates a new metastatic lesion may be used to document progression in lieu of CT/MRI/bone scan.

These patients will have their response classified according to the definitions stated below.

Measurability of the disease

Measurable lesions

Lesions that can be accurately measured in at least one dimension with longest diameter ≥ 10 mm (by CT scan, MRI, caliper measurement) or ≥ 20 mm (by chest X-ray). Pathological lymph nodes, defined as lymph nodes with a short axis >15 mm are also measurable.

Measurable disease

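### SAP 6.7 sets a 12-weekly imaging grid after week 24, while the protocol scans on-treatment patients every 8 weeks: wrong as written, minor impact

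*SAP*

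**What the plan says.** SAP 6.7 gives a single grid: "Imaging will be performed at 8, 16 and 24 weeks, and in 12-weekly intervals thereafter". Each image goes to a planned time by its study day, using a ±4-week window as appropriate. If several images land in one interval, the last is used. Treatment status is not mentioned.

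The protocol treats patients on and off treatment differently:

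- **On treatment.** Flow Chart footnote 15 and section 5.2 require imaging "every 8 weeks (+/- 1 week) calculated from the first treatment day to the end of study treatment". Section 6.2.2 has imaging "8 weeks after the start of study medication and every 8 weeks thereafter". Appendix 10.5 resembles the SAP sentence but ends differently: "patients should be re-evaluated for response at weeks 8, 16, 24 and every 8 weeks thereafter".
- **Off treatment without progression.** Section 5.2 introduces a separate schedule with "If treatment discontinuation is for other reason than disease progression, further tumour assessments should be obtained as follows": 8-weekly until month 6, then "every 12 weeks (+/-2 week) from 6 months onwards, until documented progression of disease". Footnote 15 says the same.

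SAP Section 4 lists one change to the planned analysis, the futility criterion. It does not mention imaging times.

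SAP 7.5.2 summarises time to response by planned imaging time point, after stage 2 is complete. Table 7.5.2:1, for sensitivity analyses of PFS, refers to scheduled and missed assessments without saying which schedule defines them.

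**The concern.** A 12-weekly interval does exist in the protocol, but under 5.2 and footnote 15 it applies only from month 6 and only after treatment has stopped for a reason other than progression. SAP 6.7 applies it without that condition. For a patient who stays on afatinib, the planned analysis times after week 24 (36, 48, 60 and so on) are then not the times at which scans are taken (32, 40, 48, 56, 64 and so on).

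Two things are at stake. Displays that group scans by planned time would label on-treatment scans wrongly. And if the same grid were used to count missed scans, the event or censoring status of some patients in the PFS sensitivity analysis would depend on a schedule they were not on.

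**Working it through.** The plan gives no figure to reproduce, so the check is an enumeration of days.

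**Inputs.** Planned day = 7 × week (SAP 7.4 equates 24 weeks with Day 168). SAP window: ±28 days (SAP 6.7). Protocol on-treatment window: ±7 days (footnote 15, 5.2).

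**1. SAP slots, literal ±28 days.** Week 24: 168 ± 28 = Days 140–196. Week 36: 252 ± 28 = 224–280. Week 48: 336 ± 28 = 308–364. Week 60: 420 ± 28 = 392–448. There are gaps between them, the first being Days 197–223.

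**2. Where on-time on-treatment scans fall.** Midpoints between planned SAP times are (168 + 252)/2 = 210, (252 + 336)/2 = 294, (336 + 420)/2 = 378 and (420 + 504)/2 = 462.

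| Protocol scan | On-time days | Nearest SAP time | On-time days with no slot under literal ±28 |
|---|---|---|---|
| Week 32 | 217–231 | Week 36 | 217–223 |
| Week 40 | 273–287 | Week 36 | 281–287 |
| Week 48 | 329–343 | Week 48 | none |
| Week 56 | 385–399 | Week 60 | 385–391 |
| Week 64 | 441–455 | Week 60 | 449–455 |

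Under nearest-time slotting, every on-time day of weeks 32 and 40 goes to Week 36, and every on-time day of weeks 56 and 64 goes to Week 60. Under the literal window, 7 of the 15 on-time days of each of these four scans have no slot. Weeks 72 and 96 match, as week 48 does. From week 25 to week 72 the protocol has six on-treatment scans and the SAP four slots.

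**3. Size in the time-to-response display.** Protocol 7.7 states that "70 patients would be expected to provide approximately 80% power for ORR, with ORR=15% under the alternative hypothesis and ORR=5% under the null". Expected responders in 70 patients are 0.05 × 70 = 3.5 to 0.15 × 70 = 10.5. Only those whose first response comes after week 24 can be misplaced. The documents give no timing of response, so the number may be zero. A first response at week 32 would appear 4 weeks late and one at week 40 would appear 4 weeks early, both as Week 36.

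**4. Censoring, only if the SAP 6.7 grid defines the schedule.** Take a patient still on 8-weekly scans, without progression at week 24 (Day 168), with no scans at weeks 32 and 40, who dies at week 44 (Day 308).

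- Protocol schedule: two consecutive scans missed (Days 224 and 280), death afterwards. Rule 3c: censored at week 24.
- SAP grid: one scan missed (Day 252), death before the next (Day 336). Rule 3b: event at week 44.

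The recorded time moves by 308 − 168 = 140 days and the status changes. The same holds for death or progression after the missed week-40 scan and before week 48.

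**5. Check of the remedy.** With 8-weekly planned times and the existing ±28 days, Week 32 is 224 ± 28 = 196–252, Week 40 is 280 ± 28 = 252–308 and Week 48 is 336 ± 28 = 308–364. Every on-time window lies inside its own slot. Only the boundary days 196, 252, 308 and 364 are shared.

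**The case against.** The strongest reply is that almost nothing depends on this, and most of that stands.

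- **Primary and key secondary results.** A reader might infer that PFS6 or ORR is affected. They are not. SAP 7.4 decides PFS6 on actual study days (154, 168, 182), ORR uses confirmed best response, and the futility rule counts those same outcomes.
- **Event dates.** A reader might also infer that the last-image rule overwrites a patient's response date. It does not. SAP 7.5.2 defines time to response from the date of the first documented response, and PFS and DOR likewise use dates. Only the grouping of time to response by planned time is affected.
- **Reach.** SAP 6.7 does not say that the grid applies to all patients; it simply makes no exception. Every third on-treatment scan matches. Twelve-weekly off-treatment scans under 5.2 also fit: at week 36, for example, 252 ± 14 = Days 238–266, inside 224–280.
- **Gaps.** The words *as appropriate* may be meant to avoid the unslotted days. That would close the gaps, but weeks 32 and 40 would still share one slot.
- **Censoring.** Nothing says that the slotting grid defines missed scans in Table 7.5.2:1, and SAP Section 3 refers readers to the protocol for measurement definitions. The change of status also requires a patient who is still on 8-weekly scans through week 40. This part is therefore conditional.
- **The display may never be produced.** It is made only after stage 2. At both null rates, Protocol 7.7 gives 73% and 64% for missing the two stage 1 criteria, so the chance of stopping lies between 0.73 + 0.64 − 1 = 37% and 64%, depending on how the two outcomes are related.

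None of this removes the contradiction. A programmer slots scans from SAP 6.7, and that sentence disagrees with four places in the protocol.

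**Conclusion.** SAP 6.7 is wrong as written for patients on treatment after week 24, and the impact is minor. The conflict rests on the text alone. The shared slots hold under both nearest-time and literal slotting; the days without a slot arise only under the literal reading.

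The consequence is a coarser and slightly displaced time-to-response table (4 weeks either way) for those of the 3.5 to 10.5 expected responders who first respond after week 24, possibly none. Any other by-time imaging display after week 24 would be affected in the same way.

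The documents do not support a claim that the PFS sensitivity analysis is wrong. They support only that Table 7.5.2:1 leaves its schedule unnamed, and that one possible reading would turn some censored patients into events. How often that would happen cannot be derived from the documents.

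**What to change.** 1. **SAP 6.7.** Make the planned times for patients on treatment match the protocol's on-treatment schedule, on which all four protocol places agree: 8, 16, 24, 32, 40, 48 weeks and so on. Keep the ±4-week window, which is half the interval and so leaves no gaps. State which slot owns each boundary day, for example Week 32 = Days 197–252, Week 40 = 253–308, Week 48 = 309–364.
2. **Table 7.5.2:1.** Add a line saying that *scheduled* and *missed* refer to the protocol schedule that applies to the patient at that time. Rules 1, 5, 6a and 6b concern only weeks 8 and 16, where both schedules agree, and do not change in substance.
3. **Off-treatment slots.** Protocol 5.2 and footnote 15 change the imaging interval from month 6 after discontinuation without progression, whereas Appendix 10.5 keeps the original schedule after discontinuation. These passages must be reconciled first; this review takes no position on which should stand. The off-treatment planned times and a window width that fits them can then be set.

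The cost is one or two sentences in the SAP, a protocol clarification and minor visit-window programming. The time-point table may have to carry two grids, so its layout should be decided in advance. Sample size and the primary test do not change, and items 1 and 2 leave data collection as it is.
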